5.3. Lifestyle Considerations

Potential participants must be willing and able to adhere to the following lifestyle restrictions during the study to be eligible for participation:

1. Refer to Section [6.8](#), Concomitant Therapy for details regarding prohibited and restricted therapy during the study.

It is recommended to be up to date on all age-appropriate vaccinations prior to screening as per routine local medical guidelines. It is strongly recommended that participants will have completed a locally-approved (or emergency use-authorized) COVID-19 vaccination regimen at least 2 weeks prior to study-related visits or procedures. Study participants should follow applicable local vaccine labelling, guidelines, and standards-of-care for patients receiving immune-targeted therapy when determining an appropriate interval between vaccination and study enrollment (Section [6.8](#)).
2. A woman of childbearing potential who is heterosexually active must remain on a highly effective method of birth control (Inclusion Criterion 10) during the study and for at least 12 weeks after receiving the last administration of study intervention.
3. A woman must agree not to donate eggs (ova, oocytes; Inclusion Criterion 11) during the study and for a period of at least 12 weeks following the last administration of study intervention.
4. A man who is sexually active with a female of childbearing potential and has not had a vasectomy must agree to use a barrier method of birth control (Inclusion Criterion 12) during the study and for at least 12 weeks after receiving the last administration of study intervention.
5. A man must agree to not donate sperm during the study and for at least 12 weeks after receiving the last administration of study intervention (Inclusion Criterion 13).
6. Agree to use sun protective measures (such as a hat, sunglasses, protective clothing, sunscreen), limit prolonged exposure to natural sunlight, and avoid artificial sunlight (tanning beds or phototherapy) during the study.
7. Agree to remove nail polish and/or artificial nails prior to or at all visits where nail psoriasis is assessed.
8. Agree to follow all requirements that must be met during the study as noted in the Inclusion and Exclusion Criteria (eg, contraceptive requirements).

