6.4. Study Intervention Compliance

Participant compliance with study intervention will be assessed at each visit during the treatment period by counting returned tablets.

A participant will be considered noncompliant if he or she misses more than 20% of the prescribed doses of study intervention during the study, unless study intervention is withheld for safety reasons. Similarly, a participant will be considered significantly noncompliant if he or she is judged by the investigator to have intentionally or repeatedly taken 20% or more than prescribed amount of study intervention during the study.

If a participant's study intervention intake is not according to the protocol, the investigator will take the necessary measures to ensure future adherence to the protocol. If necessary, the participant maybe discontinued from study intervention by the investigator or medical monitor (Section 7).

Study intervention compliance will be further detailed in the statistical analysis plan (SAP).

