6.8. Concomitant Therapy

Modification of an effective preexisting therapy should not be made for the explicit purpose of entering a participant into the study. Concomitant therapies must be recorded throughout the study beginning with start of the first dose of study intervention to 4 weeks after the last dose of study intervention.

All therapies (prescription or over-the-counter medications) different from the study intervention must be recorded in the eCRF. Every effort should be made to keep participants on stable concomitant medications. If a medication is temporarily discontinued because of abnormal laboratory values, side effects, concurrent illness, or the performance of a procedure, the change and reason for it should be clearly documented in the participant's medical records.

Any questions regarding treatment with concomitant medication during the study should be directed to the medical monitor.

Prohibited Therapy

All experimental therapies or new investigational interventions (except for JNJ-77242113), including therapies for psoriasis or other conditions, must be discontinued prior to the first administration of study intervention per Exclusion Criteria (Section 5.2) and remain prohibited during the study. For guidance regarding the COVID-19 vaccine see Section 6.8.1.

If a prohibited therapy is administered during the active treatment phase (ie, Week 0 to Week 16), the medical monitor should be notified, and the participant may be required to discontinue from the study treatment per medical monitor's discretion. If a prohibited therapy is initiated during the safety follow-up period, the participant should still complete his or her final study visit, and the medication should be recorded as a concomitant medication.

The sponsor must be notified in advance (or as soon as possible thereafter) of any instances in which prohibited therapies are administered.

Psoriasis Concomitant Medications

Topical Therapy

Topical therapies that could affect psoriasis or the PASI/IGA evaluation (eg, corticosteroids, tar, anthralin, calcipotriene, tazarotene, methoxsalen, pimecrolimus, tacrolimus, and traditional Taiwanese, Korean, or Chinese medicines) are not permitted during the study. The only allowable concomitant treatments throughout the study are shampoos (containing salicylic acid only) and

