7. DISCONTINUATION OF STUDY INTERVENTION AND PARTICIPANT DISCONTINUATION/WITHDRAWAL

7.1. Discontinuation of Study Intervention

A participant's study intervention must be discontinued if:

- The participant withdraws consent to receive study intervention.
- The investigator believes that for safety reasons or tolerability reasons (eg, AE) it is in the best interest of the participant to discontinue study intervention.

- The participant meets the Sampson criteria for anaphylaxis ([Sampson 2006](#)) following study intervention administration (Section [10.12](#)).
- The participant has a reaction resulting in myalgia and/or arthralgia with fever and/or rash (suggestive of serum sickness and not representative of signs and symptoms of other recognized clinical syndromes) occurring 1 to 14 days after an administration of study intervention. These may be accompanied by other events including pruritus, facial, hand, or lip edema, dysphagia, urticaria, sore throat, and/or headache.
- The participant becomes pregnant or plans a pregnancy during the study period. Refer to Section [10.8](#).
- The initiation of protocol-prohibited medications, treatments, or interventions (outlined in Section [6.8](#)) that have an impact on psoriasis efficacy evaluations at the discretion of the medical monitor.
- The participant has a malignancy including squamous cell skin cancer. Consideration may be given to allow participants, who develop ≤ 2 basal cell skin cancers and who are adequately treated with no evidence of residual disease, to continue to receive study intervention.
- The participant develops a systemic opportunistic infection during the study period.
- The participant develops a recurrent or chronic serious infection during the study period.
- The participant meets **ANY** of the following TB related conditions:
 - A diagnosis of active TB is made.
 - A participant has symptoms suggestive of active TB based on follow-up assessment questions and/or physical examination or has had recent close contact with a person with active TB and cannot or will not continue to undergo additional evaluation.

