 - A participant undergoing evaluation has chest imaging with evidence of current active TB and/or a positive IGRA test result, unless active TB can be ruled out and appropriate treatment for latent TB can be initiated prior to the next administration of study intervention and continued to completion. Indeterminate/borderline results should be handled as outlined in Section [8.2.8](#).
 - A participant receiving treatment for latent TB discontinues this treatment prematurely or is noncompliant with the therapy
- The participant is unable to adhere to the study visit schedule or comply with protocol requirements.
- The participant has a possible Hy's Law case, as defined by the occurrence of alanine aminotransferase (ALT) or aspartate aminotransferase (AST) $\geq 3 \times \text{ULN}$, together with total bilirubin $\geq 2 \times \text{ULN}$ or International Normalized Ratio (INR) > 1.5 (if measured) without an identifiable cause (Section [10.9](#)).
- The participant has his/her treatment assignment unblinded by the investigator.
- Sponsor decision.

Discontinuation of a participant's study intervention should be considered for participants with any type of suicidal ideation or behavior, or any self-injurious behavior, who are deemed to be at risk by the investigator. Discussion of such participants with the medical monitor or designee is required.

For participants who report Suicidal Ideation with Intention to Act ("Ideation level 4"), suicidal ideation with specific plan and intent ("Ideation level 5"), suicidal behavior (actual suicide attempt, interrupted suicide attempt, aborted suicide attempt, or preparatory behaviors for making a suicide attempt) or any self-injurious behavior on a post-baseline C-SSRS assessment, the investigator risk assessment must be based upon evaluation by a mental health professional (Section 10.7).

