Participants who decide to discontinue study intervention administration for reasons other than those outlined above must be interviewed by the investigator to determine if a specific reason for discontinuing study intervention can be identified. Participants should be explicitly asked about the possible contribution of AEs to their decision to discontinue study intervention; investigators should confirm that any AE information elicited has been documented. If a participant elects to discontinue study intervention due to an AE, the event should be recorded as the reason for study intervention discontinuation, even if the investigator's assessment is that the AE would not require study intervention discontinuation. The reason for study intervention discontinuation must be documented in the eCRF and in source documents. Study intervention assigned to a participant who discontinues may not be assigned to another participant.

A participant will not be automatically withdrawn from the study if he or she must discontinue treatment before the end of the treatment regimen. Participants who discontinue study intervention but do not terminate study participation will continue to return for protocol-specified procedures and evaluations for approximately 4 weeks following the last administration of study intervention. The procedures and evaluations listed for the Early Termination Visit should also be performed approximately 4 weeks after the last administration of study intervention.

All procedures and evaluations must be conducted prior to a participant's withdrawal of consent.

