7.2. Participant Discontinuation/Withdrawal From the Study

A participant will be withdrawn from the study for any of the following reasons:

- Lost to follow-up
- Withdrawal of consent
- The participant is not in compliance with requirements of the study, including prohibitions and restrictions
- Death

When a participant withdraws before study completion, the reason for withdrawal is to be documented in the CRF and in the source document. If the reason for withdrawal from the study is withdrawal of consent, then no additional assessments are allowed.

Withdrawal of Consent

A participant declining to return for scheduled visits does not necessarily constitute withdrawal of consent. Alternate follow-up mechanisms that the participant agreed to when signing the consent form apply (eg, consult with family members, contacting the participant's other physicians, medical records, database searches, use of locator agencies at study completion) as local regulations permit.

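### Protocol 7.2 lists non-compliance as a reason for withdrawal from the study, against 6.4, 6.8 and 7.1, and can needlessly lose some Week 16 PASI values

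*Protocol*

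**What the plan says.** Protocol 7.2 lists four reasons for withdrawal from the study, under a lead-in that is mandatory in form: loss to follow-up, withdrawal of consent, death, and "The participant is not in compliance with requirements of the study, including prohibitions and restrictions". The last has no threshold, leaves no discretion and is not limited to dosing.

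Other sections treat the same conduct differently:

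- **Missed or excess doses (Protocol 6.4).** If intake departs from the protocol, "the investigator will take the necessary measures to ensure future adherence to the protocol". Stopping study intervention is a further option, used if necessary.
- **Prohibited therapy during Weeks 0 to 16 (Protocol 6.8).** Here "the participant may be required to discontinue from the study treatment per medical" monitor's judgement. Protocol 7.1 repeats this for therapies "that have an impact on psoriasis efficacy evaluations at the discretion of the medical monitor". Both concern treatment only.
- **Prohibited therapy in safety follow-up (Protocol 6.8).** The participant is still to attend the final visit.
- **Inability to comply (Protocol 7.1).** "The participant is unable to adhere to the study visit schedule or comply with protocol requirements" is a reason to stop study intervention. The same section adds: "A participant will not be automatically withdrawn from the study if he or she must discontinue treatment before the end of the treatment regimen". Those who stop treatment but remain in the study "will continue to return for protocol-specified procedures and evaluations for approximately 4 weeks following the last administration of study intervention".

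The SAP uses observed PASI after treatment stops for reasons other than lack of efficacy or worsening psoriasis (intercurrent event, ICE, 3). It counts ICEs 1 and 2 as non-response, and counts a Week 16 value that is still missing as non-response (SAP 5.3.1.2.1 and 5.3.1.2.3). Analyses by visit use nominal visits (SAP 5.1.1). SAP Appendix 4 includes, among major deviations, participants who met a withdrawal criterion but were kept.

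**The concern.** A site with a non-compliant participant can follow 6.4, 6.8 or 7.1 and keep the person in the study, or follow 7.2 and withdraw them. The first choice risks being recorded as a major deviation. The second ends data collection that the estimand wants. Different sites may choose differently.

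Two analyses are affected. In the primary analysis, a participant whose breach is not ICE 1 or 2 (missed doses, fasting breaches, a live vaccine) loses a Week 16 PASI that would have been used as observed, and becomes a non-responder by rule. In Supplementary Estimand 2 (treatment policy, for pairwise PASI 75, PASI 90, PASI 100 and the two IGA endpoints), a participant who took prohibited psoriasis therapy (ICE 2) needs an imputed Week 16 value where an observed one was obtainable. For the primary analysis that participant is a non-responder either way.

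**Working it through.** **Whose Week 16 value does 7.2 lose?** Visits under 7.1 run for about 4 weeks after the last dose.

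- Stops before about Week 12: Week 16 is lost through 7.1, with or without 7.2.
- Stops at about Week 12 or later: Week 16 may still be reached. For stops near Week 12, however, the visit 4 weeks later is the Early Termination Visit (Schedule of Activities, footnote b). Under nominal visits the documents do not say that it counts as Week 16.
- Participants who would have stayed on treatment: Week 16 was scheduled and is lost only because of 7.2. This is the main group.

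**The plan's own figure.** Protocol 9.2 states at least 90% power for a 35-point PASI 75 difference, with 40 per arm, two-sided 0.05 and a two-sample Z-test. With pooled variance under the null:

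power = Φ{[Δ − 1.96·√(2p̄(1−p̄)/n)] / √[(p₁(1−p₁)+p₂(1−p₂))/n]}

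For 6% v 41%, p̄ = 0.235: (0.350 − 1.96×0.0948)/0.0864 = 1.90, so power is 97.1%. For 5% v 40% it is 97.6%, and for 10% v 45% it is 95.4%. The stated figure reproduces.

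**Effect of loss.** The documents give no rate. Assume a share d of each arm, unrelated to response, loses Week 16 and counts as non-response. Each rate p becomes p(1−d), and the difference becomes 35(1−d).

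| d | Difference (points) | Points lost | Power, 6% v 41% | Power, 10% v 45% |
|---|---|---|---|---|
| 0 | 35.0 | 0 | 97.1% | 95.4% |
| 2.5% | 34.1 | 0.9 | 96.6% | 94.6% |
| 5% | 33.3 | 1.75 | 96.1% | 93.8% |
| 10% | 31.5 | 3.5 | 94.7% | 91.9% |

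**How much of this is due to 7.2.** Let b be the share to whom 7.2 is applied for a breach that is not ICE 1 or 2, and s the share of these whose treatment would have been stopped under 7.1 anyway. If stops are spread evenly over 16 weeks, 12/16 = 75% of them lose Week 16 regardless. The loss due to 7.2 is then b(1 − 0.75s). If no late stop yields a Week 16 record, it is b(1 − s).

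| b = 10% | s = 0 | s = 50% | s = 100% |
|---|---|---|---|
| Late stops reach Week 16: b(1 − 0.75s) | 10% (4 of 40) | 6.25% (2.5 of 40) | 2.5% (1 of 40) |
| Points lost of 35 | 3.5 | 2.2 | 0.9 |
| Late stops do not: b(1 − s) | 10% | 5% | 0% |

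At b = 2.5% the first row becomes 2.5%, 1.6% and 0.6%, or 0.9, 0.5 and 0.2 points. The s = 0 column is an upper bound.

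**Unequal loss, 6% v 41%, d = 10%.** Active arm only: 0.41×0.9 − 0.06 = 30.9 points, power 93.6%. Placebo only: 0.41 − 0.06×0.9 = 35.6 points, a shift of 0.6 points towards active.

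**Dose-response test.** The max-contrast test was simulated with the six SAP candidate models, the dose labels of SAP Table 5, the logit scale and one-sided 0.025, with placebo at 6% and the top dose at 70% or 80%. Minimum power over the models is 99.9% at 10% loss in every arm and 99.7% at 20%.

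**The case against.** The best defence is that 7.2 describes a continuing state of non-compliance, and that the specific sections govern the common cases. Protocol 7.3 has sites reschedule and counsel after missed visits, and 10.3.1 has departures discussed with the sponsor. The SAP's deviation categories themselves presuppose that some such participants are kept. This is a fair account of what sites will probably do. It does not remove the conflict, because 7.2 is mandatory in form and the same SAP list marks retention as a major deviation.

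A second defence stands in part. A site strict enough to withdraw a participant would often have stopped treatment under 7.1 too, which pushes s towards 100% and the loss due to 7.2 towards 1 of 40 or less at b = 10%.

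A reader might also infer more than the documents support:

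- *That any single breach forces withdrawal, even of the restriction "Agree to remove nail polish and/or artificial nails prior to or at all visits where nail psoriasis is assessed".* Protocol 5.3 frames these items as willingness required for eligibility, and 7.2 does not say that one lapse is enough.
- *That the SAP's compliance categories (below 80%, above 120%) contradict 7.2.* They do not. The full analysis set is everyone randomized who took at least one dose, so withdrawal removes nobody from it.
- *That 7.2 causes all loss of Week 16 data after non-compliance.* For treatment stops before about Week 12, the 4-week limit in 7.1 already does.

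**Conclusion.** The inconsistency is real and its effect is low. Within the assumed 2.5% to 10% loss per arm, at most 0.9 to 3.5 points of a 35-point difference go, and less where treatment would have been stopped under 7.1 anyway. Pairwise power stays above the stated 90%. The claim that study success is at risk is not supported: the dose-response test that decides it keeps power near 100%.

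It would also be too strong to call the effect conservative without qualification. That holds for the primary non-responder analysis if loss is similar across arms or falls mainly in active arms; loss in placebo alone moves the estimate slightly the other way. The MMRM for continuous endpoints and the multiple imputation for the supplementary estimands rely on missing at random, and are not conservative by construction.

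The conclusion rests on assumed values of b and s, even timing of stops, and loss unrelated to response. None of these can be taken from the documents. The case for change is conflicting site instructions and avoidable missing data, not a threat to the result.

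**What to change.** Delete the bullet from Protocol 7.2, or replace it with: *Non-compliance is handled under 6.4, 6.8 and 7.1 and is not in itself a reason for withdrawal from the study; participants keep their scheduled visits, including Week 16 where 7.1 follow-up allows.* Making the bullet merely discretionary would remove the compulsion but would still let sites end follow-up for this reason.

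The cost is a one-bullet amendment with IEC/IRB approval and submission to the regulatory authorities, best bundled with another amendment, plus a note to sites. A protocol clarification communication would do only if no site applies 7.2 as written, since Protocol 10.3.1 limits it to text that leaves study conduct unchanged. Sites would go on following a few non-compliant participants at visits already scheduled, and treatment could still be stopped under 7.1. Recovering Week 16 after stops before about Week 12 would need longer follow-up in 7.1, which is a separate matter.

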7.2.1. Withdrawal From the Use of Research Samples

A participant who withdraws from the study will have the following options regarding the optional research sample:

- The collected sample will be retained and used in accordance with the participant's original separate informed consent for optional research samples.
- The participant may withdraw consent for optional research sample, in which case the sample will be destroyed, and no further testing will take place. To initiate the sample destruction process, the investigator must notify the sponsor study site contact of withdrawal of consent for the optional research samples and to request sample destruction. The sponsor study site contact will, in turn, contact the biomarker representative to execute sample destruction. If requested, the investigator will receive written confirmation from the sponsor that the sample has been destroyed.

Withdrawal From the Optional Research Samples While Remaining in the Study

The participant may withdraw consent for optional research samples while remaining in the study. In such a case, the optional research sample will be destroyed. The sample destruction process will proceed as described above.

Withdrawal From the Use of Samples in Future Research

The participant may withdraw consent for use of samples for research (refer to Long-Term Retention of Samples for Additional Future Research in Section 10.3.5, Appendix 3: Regulatory, Ethical, and Study Oversight Considerations). In such a case, samples will be destroyed after they are no longer needed for the clinical study. Details of the sample retention for research are presented in the main ICF and in the separate ICF for optional research samples.

7.3. Lost to Follow-up

To reduce the chances of a participant being deemed lost to follow-up, prior to randomization attempts should be made to obtain contact information from each participant, eg, home, work, and mobile telephone numbers and email addresses for both the participant as well as appropriate family members.

A participant will be considered lost to follow-up if he or she repeatedly fails to return for scheduled visits and is unable to be contacted by the study site. A participant cannot be deemed lost to follow-up until all reasonable efforts made by the study site personnel to contact the participant are deemed futile. The following actions must be taken if a participant fails to return to the study site for a required study visit:

- The study site personnel must attempt to contact the participant to reschedule the missed visit as soon as possible, to counsel the participant on the importance of maintaining the assigned visit schedule, to ascertain whether the participant wishes to or should continue in the study.
- Before a participant is deemed lost to follow-up, the investigator or designee must make every reasonable effort to regain contact with the participant (where possible, 3 telephone calls, emails, fax, and, if necessary, a certified letter to the participant's last known mailing address, or local equivalent methods). Locator agencies may also be used as local regulations permit. These contact attempts should be documented in the participant's medical records.

Should the participant continue to be unreachable, they will be considered to have withdrawn from the study.

